6.3.2.2. Analysis

Weekly average SABA use, change from week 1 in weekly average SABA use, weekly SABA-free days, change from week 1 in weekly SABA-free days, weekly total number of inhalations and inhalation attempts, and change from week 1 in total number of inhalations and inhalation attempts will be summarized using descriptive statistics.

6.3.3. Secondary Endpoint #3 – Adherence to Maintenance Treatment**6.3.3.1. Definition**

Secondary endpoint #3 is the change from baseline in adherence to maintenance treatment (FS eMDPI), defined as the proportion of actual inhalation doses taken out of the total number of inhalation doses prescribed over the 24-week treatment period. Daily adherence to maintenance treatment will be defined as $100 * (\text{number of inhalations}/2)$ if number of inhalations ≤ 2 (ie, for number of inhalations = 0, 1 and 2). Daily adherence to maintenance treatment will be defined as 100% if number of inhalations > 2 .

Weekly adherence to maintenance treatment will be defined as total daily adherence in 7 days/7. Monthly adherence to maintenance treatment will be defined as total daily adherence in 28 days/28.

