The SoC group will be followed according to the clinical judgment of the investigator; the asthma of patients in the SoC group will be managed in a manner consistent with the clinical judgement of the investigator and based on asthma management guidelines (eg, GINA). Similar to the management of the SoC group, the DS group patients will be followed by the investigational centers with the addition of objective information on FS eMDPI and Albuterol eMDPI usage being available to both patients and investigational centers through the App and the dashboard, respectively. The iHCPs will check the dashboard at least once a week and use this information, along with any other additional information about the patient, as per their clinical judgement, to modify patients' asthma management. The investigator may, if indicated, modify the patient's regime, including adding asthma controllers or biologics as otherwise clinically indicated in the judgement of the investigator. Clinically Driven Assessments for both groups, if necessary, should be arranged, per the clinical judgement of the iHCP managing the patient, and can be via a telephone call or an on-site visit.

For all patients, at Visit 2, Visit 3, and any Clinically Driven Assessments, if necessary, the iHCP will record answers to Asthma Management questions, including discussions regarding adherence, or inhaler technique, treatment adjustments, or additions of new treatments, including biologic medication usage. Additionally, in the case of a Clinically Driven Assessment (for patients in the DS group), the iHCP will be asked whether or not the contact with the patient was originated from the iHCP interaction with the dashboard.

Visit 2 (if it is an in-person visit) will include dispensing of new inhalers to the DS group patients and return of used or unused inhalers that were dispensed to the patients previously. New FS eMDPI devices will continue to be shipped directly to patients periodically after Visit 2 until the end of treatment. The ACT will be completed and scores registered.

At the end of the treatment period (24 weeks), final assessments of the DS and SoC groups will be completed, as specified in Table 5, and the rest of the inhalers that were dispensed to the DS group patients will be returned. A follow-up telephone call will be made by the investigational

center to all patients, 2 weeks later, and will confirm that the DS group patients have returned to their previous asthma treatments.

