5.1.1.1. Starting Doses and Dose Levels

CLN0035849

The prescribed dose of FS eMDPI will be 113 mcg/14 mcg or 232 mcg/14 mcg, 1 inhalation, twice daily.

The prescribed dose of Albuterol eMDPI will be 90 mcg, 1 to 2 inhalations every 4 to 6 hours, as needed. No dose escalations are planned.

Version 2.0

Page 49 of 98

Approved

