4. GENERAL ISSUES FOR DATA ANALYSIS

4.1. General

Descriptive statistics for continuous variables include n, mean, standard deviation (SD), standard error (SE), median, minimum, and maximum. Descriptive statistics for categorical variables include patient counts and percentages, missing category will be displayed as appropriate.

Treatment dates are defined as follows:

- Treatment start date: date of randomization/the screening/baseline visit date.
- Treatment end date: the end of treatment/early termination (ET) visit date. If the end of treatment/ET date is missing then the last contact date will be used.

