4.4. Study Days and Visits

Study days are numbered relative to the treatment start date (ie, ..., -2, -1, 1, 2, ...; with day 1 being the treatment start date and day -1 being the day before the treatment start date).

Weeks are defined in 7-day intervals (days 1 to 7, 8 to 14, ..., 78 to 84). Day 1 is defined as the treatment start date (i.e., date of randomization/Visit 1 visit date).

By-visit (or by-week) summaries will include baseline, and the end of treatment and ET visits. The ET visit will be summarized as a separate visit.

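### Read literally, the fixed divisors of 7 and 28 in the adherence endpoint count days after early termination, in the week or month it cuts short, as missed doses.

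*SAP*

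**What the plan says.** Secondary endpoint #3 is worded in SAP 6.3.3.1 as a ratio to what was prescribed: "defined as the proportion of actual inhalation doses taken out of the total number of inhalation doses prescribed over the 24-week treatment period". The prescription is "1 inhalation, twice daily" (Protocol 5.1.1.1), so two doses are due per full day.

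The same SAP section then gives the formula. A day scores 100 × inhalations/2, and a day with none is expressly covered ("ie, for number of inhalations = 0, 1 and 2"). More than two inhalations are capped at 100%. The sums are averaged over fixed lengths: "Weekly adherence to maintenance treatment will be defined as total daily adherence in 7 days/7" and "Monthly adherence to maintenance treatment will be defined as total daily adherence in 28 days/28". SAP 6.3.3.2 reports these values and their changes from Week 1 and Month 1, descriptively.

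Treatment has a defined end. SAP 4.1 states "Treatment end date: the end of treatment/early termination (ET) visit date", with the last contact date as fallback. At Week 24, "the rest of the inhalers that were dispensed to the DS group patients will be returned" (Protocol 3.1), and Protocol 4.3 asks for the same on withdrawal. Visit 3 is on Day 168 with a window of +3 days (Protocol Table 5 and Appendix B). The adherence formula does not use the treatment end date, and SAP 4.3, which has missing-item rules for several questionnaires, has none for inhaler data.

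**The concern.** Once the inhaler is back at the center, no study dose is due. A divisor of 7 or 28 nevertheless keeps those days in the denominator of the interval in which treatment stopped, so numerator and denominator cover different periods. The score then reflects where in the week or month the patient left, and no longer how the patient used the inhaler while having it.

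Objective #3 is about adherence patterns over time. A false low value in a patient's last interval looks like waning adherence. It also enters the SD and the minimum, both of which SAP 4.1 lists among the statistics to be reported.

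**Working it through.** The documents state no adherence figure to reproduce, so the check applies the SAP formula as written and compares it with doses taken divided by doses due.

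**Inputs**
- Daily score: 0, 50 or 100% for 0, 1 or at least 2 inhalations (SAP 6.3.3.1).
- Intervals: 7-day blocks from Day 1 (SAP 4.4). The printed list stops at Day 84 ("Weeks are defined in 7-day intervals (days 1 to 7, 8 to 14, ..., 78 to 84"); by extension Week 9 is Days 57 to 63 and Week 24 is Days 162 to 168. Months are taken as consecutive 28-day blocks, so Month 3 is Days 57 to 84 and Month 6 is Days 141 to 168.
- Dropout 10% and 388 patients (SAP 2.4), allocated 4:3 (SAP 2.2).

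**One patient: full adherence, early termination (ET) on Day 60 after one dose that day**
- Sum for Days 57 to 60: 3 × 100 + 50 = 350.
- Week 9: 350/7 = 50%. Month 3: 350/28 = 12.5%.
- Doses due: 3 × 2 + 1 = 7. Doses taken: 7. Taken out of due = 100%.

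**General case: ET on day k of an interval of length L, full adherence, one dose that day**

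Score = (100(k − 1) + 50)/L.

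| Interval | k | Score (%) |
|---|---|---|
| Week (L = 7) | 1, 2, 3, 4, 5, 6, 7 | 7.1, 21.4, 35.7, 50.0, 64.3, 78.6, 92.9 |
| Month (L = 28) | 1, 7, 14, 21, 28 | 1.8, 23.2, 48.2, 73.2, 98.2 |

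Averaged over all values of k, both come to 50%, half of the true 100%.

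**DS group means**
- DS patients: 388 × 4/7 = 221.7. At 10% dropout: about 22.
- Assume dropout spread evenly over 24 weeks and mean adherence a between 60 and 100%. A fraction 0.10/24 of the group is then cut off in any week and 0.10/6 in any month. Each such patient loses on average half of a.
- Weekly mean: 0.10/24 × 0.5 × a = 0.13 (a = 60) to 0.21 points (a = 100).
- Monthly mean: 0.10/6 × 0.5 × a = 0.50 to 0.83 points.
- With 5% dropout: about 0.06 to 0.10 weekly and 0.25 to 0.42 monthly. With 20%: 0.25 to 0.42 and 1.0 to 1.7.

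These figures keep the full DS group in the denominator throughout.

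**Completers**
- Visit 3 on Day 168, full adherence before it: Week 24 = (600 + 0, 50 or 100)/7 = 85.7, 92.9 or 100%, and Month 6 = (2700 + 0, 50 or 100)/28 = 96.4, 98.2 or 100%, for 0, 1 or 2 inhalations that day.
- Visit 3 on Days 169 to 171: the hand-back lies outside Week 24 and Month 6, so nothing changes.

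**Change from Week 1 (Day 1 is also a partial day)**
- One inhalation on Day 1: Week 1 = 650/7 = 92.9%. With one on Day 168, Week 24 is also 92.9% and the change is 0.
- Two inhalations counted on Day 1 (for example the test dose at the center described in SAP 8.2 plus a later dose): Week 1 = 100% and the change is −7.1 points.

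**The case against.** The strongest reply is that the SAP never says an incomplete week or month is calculated. A total over 7 days can be read as requiring 7 days, and Protocol 9.3 limits analyses to observed data. Where the SAP wants a value for a week without inhalations it says so, as for SABA use in 6.3.2.1.

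Only part of this stands. The SAP is indeed silent, so it is an inference that cut-off intervals will be scored. But the stated formula is the only instruction available, and the observed-data rule does not repair it: leaving unobserved days out of the sum and still dividing by 7 or 28 gives the same number as scoring them zero. Only dropping the whole interval would help, and no text says to do that. SAP 8.3 shows how it could have been said, since it leaves inhalation flow parameters undefined for a week without inhalations.

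A reader might also infer that every fully adherent completer shows a built-in fall of 7 to 14 points at Week 24, because the hand-back day is scored as missed. The documents do not support that. Inhalations taken before the visit count. Only the earliest day of the Visit 3 window lies inside Week 24. The change from Week 1 also depends on how the partial Day 1 is counted, and in the one-dose case the two partial days cancel.

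Finally, the endpoint is descriptive and DS-only, and the average effect is small. Both points stand, and they limit the weight of the concern.

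**Conclusion.** The point holds for intervals cut short by early termination. Applied as written, the formula contradicts the endpoint's own definition and can give a fully adherent patient a score anywhere from 7.1 to 92.9% for the week, or 1.8 to 98.2% for the month, with one dose on the last day. The shift in group means stays below one point at 10% dropout. That size rests on evenly spread dropout and on adherence of 60 to 100%; the documents give neither.

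One might go further and read every later week after termination as zero, which would pull the Week 24 mean down by up to 10 points at 10% dropout. The documents do not support that either. A week wholly after treatment end contains no observed data, so Protocol 9.3 leaves it out, and the SAP states no zero rule for adherence in empty weeks.

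No hypothesis test, power figure or between-group comparison is affected. Because a stated rule produces wrong individual values and is cheap to correct, it should be corrected and not left to the programmer.

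**What to change.** Amend SAP 6.3.3.1 before database lock, which SAP 2.5.2 allows:

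- Within each week or month, use as denominator the doses due from the treatment start date to the treatment end date of SAP 4.1. Keep the daily cap.
- Treat the two partial days, Day 1 and the Visit 3/ET day, in the same way, for example by excluding both from numerator and denominator. Trimming only the last day could create an artefact in the other direction: with one inhalation on Day 1 and Visit 3 on Day 168, Week 1 would stay at 92.9% and Week 24 would become 100%, a spurious rise of 7.1 points.
- Set the interval to missing below a prespecified minimum number of on-treatment days. The documents offer no basis for a particular threshold, so the sponsor should choose and state one. In the Day 60 example, excluding the ET day leaves three days in both intervals: the score is 6/6 = 100% if three days suffice, and missing otherwise.
- Extend the week list in SAP 4.4 to Day 168 and define months as 28-day blocks from Day 1.

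The cost is a wording change and one revised derivation, with no new data. The downside is that a few partial intervals become missing and, under the example rule, inhalations on the two visit days are not used.

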6.3.3.2. Analysis

Weekly adherence to maintenance treatment and change from week 1 in weekly adherence to maintenance treatment will be summarized using descriptive statistics. Monthly adherence to maintenance treatment and change from month 1 in monthly adherence to maintenance treatment will be summarized using descriptive statistics.

6.3.4. Secondary Endpoint #4 – Assessment of Behavioral Correlates of Responsiveness to Digital Health Technology**6.3.4.1. Definition**

The BMQ is used to assess cognitive representations of medicine. The BMQ-Specific (BMQ-S11) is an 11-item questionnaire that assesses representation of medication prescribed for personal use. The specific necessity subscale is the sum of items 1, 3, 5, 7, and 10, and the

specific concern subscale is the sum of items 2, 4, 6, 8, 9, and 11. The BMQ should be the second questionnaire completed during a study visit following the ACT.

The BIPQ is a 9-item questionnaire designed to rapidly assess cognitive and emotional representations of illness. The BIPQ uses a single-item scale approach to assess perception on a 0-10 response scale. The BIPQ comprises 5 items on cognitive representation of illness perception: consequences, timeline, personal control, treatment control, and identity. There are 2 items on emotional representation: concern and emotions; one item is on illness comprehensibility. The last item is on perceived cause of illness, in which respondents list the 3 most important causal factors in their illness. The cognitive subscale is the sum of items 1 to 5, and the emotional representation subscale is the sum of items 6 and 8. The BIPQ should be the third questionnaire completed during a study visit following the BMQ.

Secondary endpoint #4 is the assessment of patients' beliefs and perceptions about their disease and treatment, utilizing the BMQ and the BIPQ for both the DS and SoC groups, patients 18 years of age or older, describing their behavioral profile at baseline and at the end of the study.

6.3.4.2. Analysis

Summary statistics for the BMQ and BIPQ subscales will be presented at baseline, and the end of treatment and ET visits. BMQ and BIPQ subscales values and changes from baseline to each visit will be summarized using descriptive statistics.

6.3.5. Secondary Endpoint #5 – Evaluation of Work Productivity and Activity Impairment

6.3.5.1. Definition

The WPAI questionnaire is used to measure work productivity and activity impairment (Reilly et al 1993). Four metrics are included: absenteeism (percentage of time missed from work due to asthma in the past 7 days), presenteeism (percentage of impairment while at work due to asthma in the past 7 days), overall work impairment (aggregate of absenteeism and presenteeism), and activity impairment (percentage of impairment in daily activities due to asthma in the past 7 days). The WPAI questionnaire will be answered by patients, 18 years of age or older, at the investigational center at Visit 1, Visit 3, or at the ET visit. The WPAI questionnaire should be the 3rd questionnaire completed during a study visit following the Mini-AQLQ.

The following scores will be derived based on the WPAI questionnaire. Multiply scores by 100 to express in percentages.

- percent work item missed due to asthma: $\frac{Q2}{Q2+Q4}$
- percent impairment while working due to asthma: $\frac{Q5}{10}$
- percent overall work impairment due to asthma: $\frac{Q2}{Q2+Q4} + \left[\left(1 - \frac{Q2}{Q2+Q4} \right) \times \frac{Q5}{10} \right]$
- percent activity impairment due to asthma: $\frac{Q6}{10}$

Secondary endpoint #5 is the change from baseline measured by the WPAI questionnaire, completed by patients 18 years of age or older in both groups, at baseline and at the end of the 24-week treatment period.

6.3.5.2. Analysis

Summary statistics for the WPAI questionnaire scores will be presented at baseline, and Visit 3 and ET visits. WPAI questionnaire scores values and changes from baseline to each visit will be summarized using descriptive statistics.

6.3.6. Secondary Endpoint #6 – Usability and Acceptability of the Digital System

6.3.6.1. Definition

The SUS is used to explore device acceptability and usability for patients in the DS group. It is a 10-item tool that provides a composite measure of the overall usability of the system being studied. Responses for each item range from 1 (strongly disagree) to 5 (strongly agree). To calculate the SUS score, first sum the responses from each item. Each item's contribution will range from 0 to 4. For items 1,3,5,7, and 9 the score contribution is the response minus 1. For items 2,4,6,8 and 10, the score contribution is 5 minus the response. Multiply the sum of the scores by 2.5 to obtain the overall SUS score. SUS scores have a range of 0 to 100.

Secondary endpoint #6 is the assessment of the DS (eMDPI, App and dashboard) acceptability and usability, utilizing the SUS, completed by the patients in the DS group, 18 years of age or older, and investigational center personnel at the end of the study. The SUS will be completed after all other questionnaires.

6.3.6.2. Analysis

The SUS score (completed by patients and investigator sites) at Visit 3 and ET visits will be summarized as continuous data using descriptive statistics.

6.4.

7. MULTIPLE COMPARISONS AND MULTIPLICITY

No multiplicity adjustment is needed since there is no hypothesis testing in this study, Bayesian methods for primary endpoint and secondary endpoint #1 and descriptive nature of all other endpoints.

8. SAFETY ANALYSIS

8.1. General

In this study, safety will be assessed by qualified study personnel by evaluating reported adverse events, adverse device effects, vital signs measurements, and use of concomitant medications.

No clinical laboratory tests, physical examinations, and ECGs are scheduled to be performed during this study.

The safety analysis set will be used for all safety analyses. Summaries will be presented by treatment group and for all patients.

8.2. Duration of Exposure to IMP

Since the dosing of the test IMP is on an as-needed basis, there is no set maximum exposure.

Duration of exposure to IMP is the number of days from date of the 2nd dose (since the 1st dose is used for testing at the study site on date of randomization) to date of last dose of IMP (last dose of IMP date – 2nd dose of IMP date + 1). If the 1st dose is not used on date of randomization, the duration of exposure to IMP will be calculated as last dose of IMP date – 1st dose of IMP date + 1 assuming no testing is done at study site for the patient. Number and percent of patients will be summarized by duration of exposure to IMP categories \leq 1 week, >1 to \leq 2 weeks, ..., >23 to \leq 24 weeks, and > week 24. Duration of exposure to IMP (days) and number of inhalations will also be summarized as continuous data using descriptive statistics.

The number of days a patient takes IMP will be summarized as continuous data using descriptive statistics. If a patient takes more than 1 IMP treatment on the same day, the patient will be counted only once in the summary; if a patient does not take any IMP treatment on a given day the patient will be counted as zero on that day. Summaries will be presented separately for FS eMDPI and Albuterol eMDPI.

8.3. Inhalation Flow Parameters

Inhalation flow parameters (peak inhalation flow [PIF], inhalation volume, inhalation duration, and time to PIF) values will be calculated for each week in the treatment period. This will be done separately for FS eMDPI and Albuterol eMDPI.

The inhalation parameters for each week are defined as the values from the inhalation with the median value of PIF during each week. If the number of inhalations is an even number, the later of the two inhalations in the middle will be deemed as the inhalation for the week. If no inhalations are done in a week, no inhalation parameters are defined for the week. Similarly the inhalation parameters for the entire 24-week treatment period are the values from the inhalation with the median PIF during the entire 24-week treatment period. Any inhalation with PIF > 120 L/min will be excluded from derivations.

Summary statistics for inhalation flow parameters will be presented by week in the treatment period, and the entire 24-week treatment period. Actual values and changes from week 1 to each week and overall will be summarized using descriptive statistics.

Statistical analyses of inhalation flow parameters will be performed outside of the scope of this SAP. The big data team will analyze this data and a separate SAP will be developed for this.

8.4. Adverse Events

All adverse events will be coded using the MedDRA. Adverse events occurring on or after the treatment start date will be included in the summary tables while all of the adverse events will be listed in data listings.

A summary will be presented for adverse events in the following categories: all adverse events, adverse events determined by the investigator to be related to study drug, severe adverse events, serious adverse events, adverse events leading to withdrawal from the study, non-serious adverse events, device-related adverse events (DS group only), asthma related adverse events, and CAE related adverse events. The incidence of patients with an adverse event in each category will be summarized using descriptive statistics.

Summaries will be presented for all adverse events (overall and by severity), adverse events determined by the investigator to be related to study drug (overall and by severity), serious adverse events, adverse events leading to withdrawal from the study, non-serious adverse events, and device-related adverse events (DS group only).

The incidence of adverse events will be summarized using descriptive statistics by SOC and preferred term (all AEs overall will also be presented by just preferred term category). Patients are counted only once in each SOC category, and only once in each preferred term category. For the summaries by severity, patients are counted at the greatest severity. Adverse events with the missing flag indicating serious will be excluded from the summary of serious adverse events but included in the summary of non-serious adverse events.

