7.1.2. Recording and Reporting of Adverse Events

For recording of an adverse event, the study period is defined for each patient as the time period from signature of the ICF to the end of the follow-up period (end of study [follow-up telephone call]). The period for reporting treatment-emergent adverse events is defined as the period after the first dose of IMP is administered and until the end of the follow-up period.

All adverse events that occur during the defined study period must be recorded both on the source documentation and the CRF, regardless of the severity of the event or judged relationship to the IMP. For serious adverse events, the serious adverse event form must be completed, and the serious adverse event must be reported immediately (Section 7.1.5.3.1). The investigator does not need to actively monitor patients for adverse events after the defined period.

At each contact with the patient, the investigator or designee must question the patient about adverse events by asking an open-ended question such as "Have you had any unusual symptoms or medical problems since the last visit? If yes, please describe." All reported or observed signs and symptoms will be recorded individually, except when considered manifestations of a medical condition or disease state. A precise diagnosis will be recorded whenever possible. When such a diagnosis is made, all related signs, symptoms, and any test findings will be recorded collectively as a single diagnosis on the CRF and, if it is a serious adverse event, on the serious adverse event form.

The clinical course of each adverse event will be monitored at suitable intervals until resolved, stabilized, or returned to baseline; or until the patient is referred for continued care to a healthcare professional; or until a determination of a cause unrelated to the IMP or study procedure is made.

The onset and end dates, duration (in case of adverse event duration of less than 24 hours), action taken regarding IMP, treatment administered, and outcome for each adverse event must be recorded both on the source documentation and the CRF.

The relationship of each adverse event to IMP and study procedures, and the severity and seriousness of each adverse event, as judged by the investigator, must be recorded as described below.

Further details are given in the Safety Monitoring Plan.

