- absence of initial findings of cholestasis (ie, no substantial increase of alkaline phosphatase)

An adverse event that does not meet any of the criteria for seriousness listed above will be regarded as a nonserious adverse event.

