7.1.5.3. Reporting a Serious Adverse Event

7.1.5.3.1. Investigator Responsibility

To satisfy regulatory requirements, all serious adverse events that occur during the study, regardless of judged relationship to administration of the IMP, must be reported to the sponsor by the investigator. The event must be reported within 24 hours of when the investigator learns about it. Completing the serious adverse event form and reporting the event must not be delayed, even if not all the information is available. The investigator does not need to actively monitor patients for adverse events once this study has ended.

Serious adverse events occurring to a patient after the last administration of IMP of that patient has ended should be reported to the sponsor if the investigator becomes aware of them.

The serious adverse event form should be sent to the local safety officer (LSO) or designee (a CRO in a country without a sponsor LSO) (contact information is in the Clinical Study Personnel Contact Information section); the LSO will forward the report to the sponsor's GPSP.

The following information should be provided to record the event accurately and completely:

- study number
- investigator and investigational center identification
- patient number
- onset date and detailed description of adverse event
- investigator's assessment of the relationship of the adverse event to the IMP (no reasonable possibility, reasonable possibility)

61

Additional information includes:

- age and sex of patient
- date of first dose of IMP
- date and amount of last administered dose of IMP
- action taken
- outcome, if known
- severity

- explanation of assessment of relatedness
- concomitant medication (including doses, routes of administration, and regimens) and treatment of the event
- pertinent laboratory or other diagnostic test data
- medical history
- results of dechallenge/rechallenge, if known
- for an adverse event resulting in death
 - cause of death (whether or not the death was related to IMP)
 - autopsy findings (if available)

Each report of a serious adverse event will be reviewed and evaluated by the investigator and the sponsor to assess the nature of the event and the relationship of the event to the IMP, study procedures, and to underlying disease.

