9.7. Safety Analysis

Safety analyses will be performed using the safety analysis set. For categorical variables, patient counts and percentages will be provided.

Safety assessments and time points are provided in Table 5.

All adverse events will be coded using the Medical Dictionary for Regulatory Activities (MedDRA). Each patient will be counted only once in each preferred term or System Organ Class category for the analyses of safety. Summaries will be presented for all adverse events (overall and by severity), adverse events determined by the investigator to be related to test IMP (ie, reasonable possibility; defined as related or with missing relationship [Section 7.1.4]; overall; and by severity), serious adverse events, adverse events causing withdrawal from the study, and adverse device effects. Summaries will be presented by treatment group and for all patients. Patient listings of serious adverse events and adverse events leading to withdrawal will be presented.

Changes in vital signs measurements data will be summarized descriptively. All values will be compared with predefined criteria to identify potentially clinically significant values or changes, and such values will be listed.

The use of concomitant medications will be summarized by therapeutic class using descriptive statistics.

For continuous variables, descriptive statistics (n, mean, SD, median, minimum, and maximum) will be provided for observed values and changes from baseline to each time point. For categorical variables, patient counts and percentages will be provided. Descriptive summaries of serious adverse events, patient withdrawals due to adverse events, adverse device effects, and potentially clinically significant abnormal values (vital signs) based on predefined criteria will be provided as well.

If any patient dies during the study, a listing of deaths will be provided, and all relevant information will be discussed in the patient narrative included in the CSR.

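### SAP 8.4 tabulates adverse events with a blank seriousness flag as non-serious, so the rule can only lower the reported serious-event incidence or leave it unchanged

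*SAP*

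**What the plan says.** The rule is the last sentence of SAP Section 8.4. Its first half reads "Adverse events with the missing flag indicating serious will be excluded from the summary of serious adverse events"; its second half continues "but included in the summary of non-serious adverse events". An event with unknown seriousness is therefore placed in the non-serious summary, not merely left out of the serious one.

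The protocol has no rule for missing seriousness. Three of its statements bear on the point:

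- At the end of the definition of a serious adverse event (Section 7.1.5.1): "An adverse event that does not meet any of the criteria for seriousness listed above will be regarded as a nonserious adverse event".
- On recording (Section 7.1.2): "the severity and seriousness of each adverse event, as judged by the investigator, must be recorded as described below".
- On missing relationship, a different attribute of the same events (Section 9.7, and likewise the synopsis), related events are "defined as related or with missing relationship".

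The SAP's own text on related events in Section 8.4 does not repeat that last convention. It refers only to "adverse events determined by the investigator to be related to study drug (overall and by severity").

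The SAP Introduction gives the SAP precedence where it differs from the protocol. SAP Section 11, which lists changes from the protocol, does not mention the seriousness rule, and no reason for it is given elsewhere.

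**The concern.** The rule treats not known as no. An event is nonserious under the protocol once it has been found to meet none of the listed criteria. A blank field records no such finding.

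Where the protocol does state a convention for a missing safety attribute, namely relationship, it places the event in the more cautious category. The SAP does the reverse for seriousness without explanation.

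Safety of the two inhalers is secondary objective #7. Serious events are foreseeable in this population: the protocol's definition of a clinical asthma exacerbation (Section 7.1.1) includes in-patient hospitalization for asthma. If serious events turn out to be few, moving even one between tables could be visible to a reader of the clinical study report.

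**Working it through.** The plan gives no figure to reproduce and no count of expected blanks, so the check compares texts and then works out the direction of the rule algebraically.

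**1. Does a blank flag satisfy the protocol's definition of nonserious?** The definition requires that no seriousness criterion is met. A blank flag is compatible with a criterion being met and with none being met. It establishes neither.

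**2. In which direction does the rule act?** SAP 8.4 counts patients, each once per system organ class and once per preferred term. For one row of the table in one arm, taking completed flags as correct, let:

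- S = patients with at least one event flagged serious;
- M = patients with a blank-flag event and no event flagged serious;
- T = those among the M whose blank-flag event was in fact serious, so 0 ≤ T ≤ M.

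| Quantity | Serious-event row |
|---|---|
| SAP rule | S |
| Counting blanks as serious | S + M |
| True number | S + T |

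The SAP figure minus the true figure is S − (S + T) = −T, which is zero or negative. Counting blanks as serious gives (S + M) − (S + T) = M − T, which is zero or positive. The SAP rule always reports the lower bound of the serious row. By the same reasoning it reports the upper bound of the non-serious row. A patient who already has a flagged serious event in the row is in S, so an additional blank for that patient changes nothing.

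**3. How does this compare with the relationship convention?**

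| Missing attribute | Where stated | Event is counted as |
|---|---|---|
| Relationship | Protocol 9.7 and synopsis: "reasonable possibility; defined as related or with missing relationship" | related |
| Seriousness | SAP 8.4: "but included in the summary of non-serious adverse events" | non-serious |

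The directions differ. The variables also differ, and both rules can be applied to the same event without contradiction.

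**4. How many blanks will reach the tables?** The documents do not say. The steps that should keep M low are:

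- the duty to record seriousness, and a separate serious adverse event form for each serious event (Protocol 7.1.2);
- expedited reporting: "The event must be reported within 24 hours of when the investigator learns about it" (Protocol 7.1.5.3.1);
- queries to the center for missing data (Protocol Appendix G, Data Quality Control).

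Appendix G also has data from external sources compared with the database, but it does not name serious adverse event reports among them. As written, an event reported on a serious adverse event form but left blank in the analysis flag would be tabulated as non-serious.

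**The case against.** The best defence is that this is an open, pre-specified convention with little to act on. A truly serious event would have to keep a blank flag through mandatory recording, its own form, 24-hour reporting, joint review by investigator and sponsor, and data queries. Even then it would still appear in the all-event tables, the severity tables and the listings. Serious events are also reviewed during conduct as they are reported (Protocol 3.4), whatever the tabulation rule. Finally, counting every blank as serious has an error of its own: a blank no more proves seriousness than it disproves it, and the serious table could then disagree with the serious events actually reported.

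Most of this stands. It shows that the effect is likely to be small and that reconciliation should come before any default. It does not justify the default. The rule applies only to flags that remain blank after those safeguards, and for them the safeguards give no reason to prefer non-serious. The risk of overstatement is met by a footnote or a separate row.

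Two stronger readings are tempting, and the documents do not support them.

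- A reader might infer that SAP 8.4 contradicts Protocol 9.7. It does not: one rule concerns seriousness and the other causality, and the protocol is silent on missing seriousness.
- A reader might infer that each blank flag understates the true serious count by one. That requires the event to have been serious and the patient to have no other flagged serious event in the same row. Neither can be assumed.

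**Conclusion.** The point holds as a minor, one-directional weakness in a tabulation rule. SAP 8.4 assigns unknown seriousness to the non-serious table without support from the protocol's definition, and it can only lower the tabulated serious-event incidence or leave it unchanged.

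The size cannot be stated from the documents. It is T patients per row, between zero and the number of patients with a residual blank and no flagged serious event. With no residual blanks the effect is zero, which is quite possible. Any percentage would need assumed numbers of serious events and blanks, and an assumption that the blank-flag events were serious.

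The conclusion assumes that completed flags are correct and that the flag is a field expected to hold a recorded answer. The SAP's description of it as missing supports the second assumption, though the case report form is not among the documents. The conclusion does not depend on the serious-event table having special status among the safety outputs. The documents assign it none; secondary endpoint #7 covers adverse event and adverse device effect data generally.

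**What to change.** Replace the last sentence of SAP Section 8.4 with:

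> Missing seriousness flags will be queried and reconciled with the reported serious adverse events before database lock; any event whose flag is still missing will not be counted as non-serious but will be included in the serious adverse event summary with a footnote giving the number of such events (or shown as a separate missing row).

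Reconciliation does most of the work, since it recovers any event already reported as serious. The footnote lets a reader see both bounds, S and S + M, where they differ.

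The cost is one sentence, plus a comparison of the event records with the serious event reports before lock. The downside is that a few events that were not serious may appear in the serious table, identified by the footnote; the separate-row option avoids this.

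In the same edit, restate the protocol's missing-relationship convention in SAP 8.4, so that both missing-data rules for adverse events stand in the document that governs the tables.
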